- I6. ≥3 clinically relevant asthma exacerbations⁴⁶ in the past two years or ≥2 clinically relevant asthma exacerbations in the past year or ≥1 severe asthma exacerbation⁴⁷ in the past year prior to randomisation while being on asthma controller medication (low dose ICS plus LABA or medium/high dose ICS with or without LABA)⁴⁸. The asthma controller medication at the screening visit must be at a dose equivalent to or below the dose the subject received before the last asthma exacerbation occurred
- 17. One or more of the following within the past 4 weeks prior to randomisation:
 - a. Daytime asthma symptoms more than twice/week
 - b. Any nocturnal awakening due to asthma which require use of SABA rescue medication
 - c. SABA rescue medication needed for treatment of asthma symptoms more than twice/week
 - d. Any activity limitation due to asthma
- I8. Lung function measured by FEV₁ ≥ 70% of predicted value⁴⁹ or according to local requirements while on background treatment following at least a 6-hour washout of SABA at screening and randomisation
- 19. Clinical history of HDM AR within the last year prior to randomisation⁵⁰
- I10. An average TCRS>0 during the baseline period (period 2)
- I11. Positive specific IgE (defined as ≥class 2, ≥0.70 kU/I) against *D. pteronyssinus* and/or *D. farinae* at screening
- 112. Positive SPT⁵¹ to *D. pteronyssinus* and/or *D. farinae* at screening
- 113. Subject willing and able to comply with trial protocol

⁴⁹ Interpretation of normal range for spirometric test should be based on the Quanjer reference equations (Quanjer et al. 1995).

⁴⁶ A clinically relevant asthma exacerbation is defined as at least one of the following criteria: a) Doubling of ICS dose compared to background treatment, b) Systemic corticosteroids for treatment of asthma symptoms for at least 3 days, c) Emergency room visit due to asthma, requiring systemic corticosteroids or d) Hospitalisation for more than 12 hours due to asthma, requiring treatment with systemic corticosteroids.

⁴⁷ A severe asthma exacerbation is defined as at least one of the following: a) Systemic corticosteroids for treatment of asthma symptoms for at least 3 days, b) Emergency room visit due to asthma, requiring systemic corticosteroids or c) Hospitalisation for more than 12 hours due to asthma, requiring treatment with systemic corticosteroids.

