⁴⁸ One asthma exacerbation within the last year must be documented including asthma medication and dosage immediately prior to this exacerbation.

⁵⁰ If medical records are not available, verbal history from subject/parent/caregiver can be used to fulfill this criterion and this must be documented in the medical records by the investigator.

⁵¹ A positive SPT is defined in the SPT Guideline. Briefly, for subjects in North America, a positive SPT is defined as a wheal size \geq 5 mm larger than the negative control. For subjects in Europe, a positive SPT is defined as a wheal size \geq 3 mm.

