11.5 Medical history

The relevant medical history, incl. diseases present at trial entry must be recorded in the eCRF.

The asthma history should include a detailed description of all asthma exacerbations including information on visits to emergency rooms, hospitalisations and changes in asthma treatment during the past 2 years. In addition a detailed allergy history including recording of the subject's history of rhinitis, conjunctivitis, atopic dermatitis and food allergy.

Information on exposure to cigarette smoke will be collected.

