### 4.2.3 Main analytical approach

The primary endpoint, based on both the primary and secondary estimand, will be compared between treatment groups using the hypothetical estimand for the FAS population using either the DPS1 or DPS2, i.e. subjects for whom the primary endpoint is missing due to discontinuation of treatment prior to period 4 will not contribute to the analysis. This approach of using observed data only (an observed case analysis), implicitly assumes that observations are missing completely at random (MCAR), i.e. had the subjects continued treatment into the efficacy assessment period (period 4), they would have experienced the same treatment effect as subjects from the same treatment arm with observations of the primary endpoint. This assumption will be investigated in a sensitivity analysis.

The primary endpoint will be analysed by means of a negative binomial (NB) regression model with the number of asthma exacerbations as the response variable, treatment group, age group (<12 years/ $\geq$ 12 years) and region as fixed effects, and the logarithm of the time in period 4 (in years) as an offset value.

The between treatment group comparison will be performed using a Log Likelihood Ratio (LR) test derived from the NB regression analysis. The null hypothesis is that the rate of clinically relevant asthma exacerbations is equal for the active group and the placebo group. The alternative hypothesis is that the rate of clinically relevant asthma exacerbations is different for the active

Type of document Document ID	Date: Version:	11-Aug-2022 4.0	
	Status:	Final	
	гауе.	310179	

group and the placebo group. The main outcome is the resulting p-value from the LR test reported together with the ratio of the rates and Wald 95% confidence intervals.

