### 4.3.1.3 Main analytical approach

The key secondary endpoints will be compared between treatment groups using the primary estimand for the FAS population.

The proportion of days with nocturnal awakening which require SABA rescue medication over the 14 days eDiary assessment period (before V5, V6, V7, V8, V9, V10 and V11) will be modelled by a marginal logistic regression model with an unstructured working covariance matrix. The response variable is the number of days with nocturnal awakenings due to asthma requiring SABA rescue medication out of the total number of days recorded. Treatment, visit and treatment-by-visit interaction, age group (<12 years/≥ 12 years) and region will be included as fixed effects. Baseline proportions of nocturnal awakenings requiring SABA will be included as a covariate. The marginal model will be estimated using a generalized estimating equations (GEE) approach. The treatment effect on the logit scale is an average treatment effect across all visits and will be estimated as a contrast of parameters in the marginal model. For both the overall treatment effect and the effect per visit, the corresponding odds ratio for proportions of days with nocturnal awakening requiring SABA of active treatment relative to placebo will be presented together with the coherent p-value and 95% confidence limit.

The proportion of days with SABA use over the 14 days eDiary assessment period (before V5, V6, V7, V8, V9, V10 and V11) will be analysed by means of a marginal logistic regression model and a GEE estimation approach as described for "proportion of days with nocturnal awakening which require SABA".

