Percentage predicted FEV1 assessed every 4 months after randomisation (at V5, V6, V7, V8, V9, V10 and V11) will also be analysed by means of an MMRM model. The response variable is the percentage predicted FEV1. Treatment, visit, treatment-by-visit interaction, age group (<12 years/ $\geq$  12 years) and region will be included as fixed effects. Baseline percentage predicted FEV1 (measured at visit 3) will be included as a covariate. Different residual errors for each treatment group will be specified and the within-subject correlated errors are modelled by an unstructured covariance. The treatment effect is the average treatment effect across all visits. The between treatment comparison will be performed by means of a t-test with Kenward-Roger degrees of freedom approximation (Kenward and Roger 1997). For both the overall treatment effect and the effect per visit, the resulting p-value will be reported together with the difference in adjusted means.

In addition, the absolute treatment estimates by visit and 95% confidence intervals will be plotted from the MMRM model.

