#### 7.1.4 Imputation of dates

When establishing how many historical asthma exacerbations a subject has within a given period, a partial end date is imputed to be as late as possible but no later than the date of informed consent.

When calculating the duration of medical history of asthma or rhinitis, a partial start date is imputed to be as early as possible.

For the purpose of defining which adverse events are treatment emergent or calculating a duration, any partial start date is imputed of the adverse event is imputed to be as early as possible, if the start date could possibly be the date of first dose of IMP given the partial date and the end date if any, it is instead imputed to be the date of first dose.

Any partial date of last dose is imputed to as late as possible but no later than the date of last contact. Missing dates of last dose are imputed as the date of last contact.

To be able to calculate the age at the start of a given diary period, the partial date of birth of each subject is imputed to be as late as possible taking the age at screening, the date of screening, the age recorded for pulmonary function tests at baseline, and the corresponding date into consideration.

Type of document Document ID	Date: Version:	11-Aug-2022 4.0	1.1	
	Status:	Final		
INTERNAL USE	Page:	56 of 79		

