#### SAS Code

proc genmod data=a;

class treat agegroup region;

model aval = treat agegroup region/ link=log dist=negbin offset=log\_time;

Ismeans treat/ cl means exp diff ;

run;

/pe of document ocument ID	Date: Version:	ate: 11-Aug-2022 ersion: 4.0	
	Status:	Final	
INTERNAL USE	Page:	59 of 79	

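### The primary negative binomial model omits baseline exacerbation history, which the trial already collects, while the key secondary models adjust for baseline: a modest loss of precision whose size the documents do not fix

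*SAP*

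**What the plan says.** SAP 4.2.3 specifies a negative binomial model "with the number of asthma exacerbations as the response variable, treatment group, age group" and region as fixed effects, with the log of time in period 4 as offset. The code in SAP 7.2.5 agrees: "model aval = treat agegroup region/ link=log dist=negbin". Protocol 15.8 has the same structure with country in place of region. The sensitivity, per-protocol and subgroup analyses (SAP 4.2.4, 4.2.5, 4.6.2) reuse this model, and none of them adds history.

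The history itself is available:
- Protocol 11.5: "The asthma history should include a detailed description of all asthma exacerbations", covering the past 2 years.
- Protocol 4.1, criterion I6, admits children by their past count: at least three clinically relevant events "in the past two years or ≥2 clinically relevant asthma exacerbations in the past year or" at least one severe event in the past year, with the period ending at randomisation. A footnote adds: "One asthma exacerbation within the last year must be documented including asthma medication and dosage immediately prior to this exacerbation".
- SAP 7.1.4 has a rule for counting historical exacerbations within a period: "a partial end date is imputed to be as late as possible but no later than the date of informed consent".

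The key secondary models in SAP 4.3.1.3 do adjust for baseline. For nocturnal awakenings, "Baseline proportions of nocturnal awakenings requiring SABA will be included as a covariate". The model for SABA days is defined by reference to that one. For percentage predicted FEV1, the baseline value is "measured at visit 3) will be included as a covariate".

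**The concern.** SAP section 5 describes overdispersion as some subjects tending to have more exacerbations than others. In the trial's own sample size formula this between-subject variation is the 2k term, and a baseline count is the collected variable best placed to reduce it. The plan gives no reason for adjusting the key secondary endpoints for baseline but not the primary one.

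Precision is short. The first SSR arrived at 900 subjects for 81% power (SAP 5.1), 533 were randomised (SAP 1.2), and the second SSR was not done (SAP 4.8). The primary test also gates the three key secondary tests (SAP 2.1).

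**Working it through.** **Inputs from the documents**
- RR=0.70 (Protocol 15.2.1); two-sided alpha 0.05 (SAP 4.1).
- Planning: 0.64×52/24=1.387 events per year, 86 weeks, k=0.7, 30% drop-out (SAP 5).
- SSR: 450 per arm gives 81% power (SAP 5.1).
- Subjects: 533 less 9 at site 613 (SAP 3.1) = 524 = 76+249+199 (Protocol Table 14), so 262 per arm if split equally.
- Share entering period 4 in cohorts 1 and 2: (72+244)/(76+249)=0.972 (Table 14).

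**Assumption, not in the documents:** history explains a fraction f of k, with f from 3% to 16%. This corresponds to a past-future log-rate correlation of about 0.3 to 0.7. Simulation with log-normal rates, I6 applied and half of events taken as severe gave 2.0%, 6.4% and 13.9% at correlations 0.3, 0.5 and 0.7. Variants for under-recording, late date imputation and a lower future rate ranged from 1.2% to 18.5%.

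**Step 1. Reproduce the plan's figure.** With μ1=2.293 and μ2=1.605:

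N = {(1.282+1.960)/ln(1/0.7)}² × {1/2.293+1/1.605+1.4} = 82.59×2.459 = 203.1 per arm, against 202 stated. Here 2k is 1.4/2.459=57% of the variance bracket.

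**Step 2. Bracket implied by the SSR result.**

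B = 450×0.972×0.3567²/(0.878+1.960)² = 6.91.

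The SSR formula gives B = 2.89/(1.4×rate×608/365)+2k. One number cannot identify both k and the rate, so each k has its own rate. This takes the full 608 days for every child who enters period 4. Early IMP discontinuation would shorten that time and raise the implied rates.

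**Step 3. Power with the history term.**

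Power = Φ(0.3567×√(262×0.972/(B−2kf))−1.96). The equivalent gain in subjects is B/(B−2kf)−1.

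| k | 2k share of B | Implied rate/year | f=0 | f=3% | f=16% | Equivalent extra subjects |
|---|---|---|---|---|---|---|
| 0.7 | 20% | 0.22 | 58.1% | 58.4% | 59.5% | 0.6-3.3% |
| 1.4 | 41% | 0.30 | 58.1% | 58.7% | 61.0% | 1.2-6.9% |
| 2.0 | 58% | 0.43 | 58.1% | 58.9% | 62.3% | 1.8-10.2% |

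The factor 0.972 cancels at f=0 and hardly matters otherwise: at k=0.7 and f=16%, power is 59.7% with 0.90 and 59.5% with 1.0.

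**Step 4. Other bases.**
- Planning inputs (B=2.459, 262×0.7 per arm): 86.9% to 87.4-89.8%.
- Half the SSR-implied rate at k=0.7, an assumption prompted by SAP 5.1, which expects Covid-19 to reduce exacerbations: B=2×(6.91−1.4)+1.4=12.42, and power goes from 36.5% to 36.6-37.1%.

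**Step 5. Effect on the estimate.** In simulated trials on the planning inputs with 210 per arm, the mean log rate ratio was about −0.36 both with and without a prognostic covariate. Only the standard error changed.

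**The case against.** The case for leaving the model alone is a fair one.

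- **No error is involved.** The model follows Protocol 15.8. Age group is the only stratification-type factor at randomisation (SAP 1.2.3), and region is named as an expected source of variation (SAP 4.1.1). This stands. A reader might infer that the omission biases the rate ratio or inflates the type I error. Nothing in the documents supports that, since treatment is randomised and the test is valid without the term.
- **The gain may be negligible.** This stands for k=0.7 and for lower rates. A reader might go further and infer from the SSR that the 57% share on the planning inputs is too high. That does not follow: the SSR's k and rate are unpublished, and k=2.0 with 0.43 events per year gives the same bracket with a 58% share. SAP 5.1 itself doubts the SSR because observations were few.
- **The size rests on assumed prognostic strength.** This stands. If history explained 30% of k and k were 2.0, the bracket would fall to 6.91−1.2=5.71 and power would be about 66%. Pandemic conditions could instead weaken prediction: Table 14 shows no pre-Covid period 4 time for cohort 3.
- **The comparison with the key secondary models is loose.** Their baselines are measured prospectively, whereas history is retrospective, truncated by I6 and only partly documented. That reduces the likely gain. Error in a pre-randomisation covariate does not bias the treatment comparison.
- **It is late.** SAP v4.0 is final, dated 11-Aug-2022. But SAP section 1 says approval preceded unblinding, and SAP 4.8 records comparable model changes.

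**Conclusion.** The point holds as a low-cost improvement in precision. The primary model leaves out the collected baseline variable closest to its endpoint, and the plan does not say why. On the SSR basis the gain is about 0.3 to 4 percentage points of power, depending on k (0.7 to 2.0) and on history explaining 3-16% of it. On the planning inputs it is about 0.5 to 3 points. These figures assume RR=0.70, 262 per arm and the trial's closed formula. The documents fix neither k at the SSR nor the strength of history, so no single figure should be quoted. A reader might also infer that adjustment would rescue the trial's power. Within the assumed range it would not: the highest SSR-basis value is 62.3%.

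**What to change.** Before unblinding, add one term to the primary negative binomial model and to the sensitivity, per-protocol and subgroup versions that reuse it: log(count+1) of clinically relevant exacerbations in the year before randomisation.

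- **Window:** use the I6 window, combining the visit 1 history with exacerbations recorded from screening to visit 3. Counting back from consent would not match the eligibility rule, because screening may precede randomisation by up to 12 weeks.
- **Partial dates:** apply the SAP 7.1.4 rule to the visit 1 history.
- **Missing history:** set a treatment-independent rule on the same window, for example the smallest past-year count implied by the I6 route met. That is two for the two-in-a-year route and one for the severe-event route. It is also one for the two-year route, through the documentation footnote, if its year is likewise read as ending at randomisation.
- **Reporting:** keep the currently specified model as a supportive analysis and list the change in SAP 4.8.

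With a log link and no treatment interaction, the rate ratio keeps its meaning. The cost is one parameter, one derived variable and a small late departure from Protocol 15.8. The covariate carries measurement error, since only one past-year event must be documented and late imputation can pull uncertain events into the window. If unblinding has already occurred, report the adjusted model only as a labelled supplementary analysis.

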Period 2 is the baseline period of 3 weeks following screening. For cohort 1, the baseline period is during Q1 - Q2 2018. For cohort 2, the baseline period is during Q4 2018 - Q2 2019. For cohort 3, the baseline period is during Q4 2019 - Q2 2020. For cohort 4, the baseline period will occur during Q4 2021 – Q2 2022. During the baseline period, eligible subjects or their parent/caregiver will fill in their asthma and rhinoconjunctivitis symptoms and medication use in an eDiary. Subjects will continue with their regular asthma background treatment. The subjects' regular asthma rescue mediation and rhinoconjunctivitis rescue medication must be replaced with the rescue medication provided by ALK at visit 2 with the exception of additional sponsor provided ICS, which is optional.

Period 3 is the treatment initiation and maintenance period to allow the treatment with the HDM SLIT-tablet to take effect. It starts at randomisation and lasts for at least 4 months. The period ends on 1 September 2018 for cohort 1, on 1 September 2019 for cohort 2, on 1 September 2020 for cohort 3 and on 1 September 2022 for cohort 4.

During the first 28 days of period 3, prespecified symptoms⁴⁰ occurring after IMP intake will be recorded by the subject/parent/caregiver in the eDiary. The reported symptoms will be evaluated by investigator and reported in the eCRF as solicited AEs.

Period 4 is the efficacy assessment period. Period 4 lasts until the end of trial or discontinuation from the IMP⁴¹ and during this period the rate of clinically relevant asthma exacerbations will be

⁴⁰ AEs identified by the World Allergy Organization (WAO) as local side effects of SLIT (Passalacqua et al. 2013).

⁴¹ Subjects will be discontinued from the IMP treatment after 2 severe asthma exacerbations in 12 consecutive months or 1 hospitalisation due to asthma requiring treatment with systemic corticoteroids.

evaluated from 1 September 2018 to 30 April 2020 (cohort 1), 1 September 2019 to 30 April 2021 (cohort 2), 1 September 2020 to 30 April 2022 (cohort 3) and 1 September 2022 to 30 April 2024 (cohort 4).

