### 3.2 Impact of Covid-19

Covid-19 has impacted the trial in terms of both recruitment opportunities and impact on the primary endpoint, see section **5.1**.

Additional statistical analyses of the primary endpoint (see section **4.2.6**) and the key secondary endpoints (see section **4.3.1.6**) are performed to analyse the impact of Covid-19.

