### 4.1 General considerations

If nothing else is mentioned, all the statistical tests described in this section use a significance level of 5% and all tests and confidence intervals are 2-sided. The null hypothesis is the hypothesis of no difference and the alternative to the null hypothesis is the hypothesis of difference.

Descriptive statistics for numerical variables include summary tables displaying mean, SD, median, minimum and maximum and relevant quantiles. Descriptive statistics for categorical variables include frequency tables that display numbers and percentage.

When age is used as fixed effect in the statistical models, it is the age assessed at randomisation that is used.

Type of document	Date:	11-Aug-2022	
Document ID	Version:	4.0	
	Status:	Final	
INTERNAL USE	Page:	29 of 79	

If baseline measurements are missing for any efficacy endpoints, the last measurement before or on the date of first treatment will be used, if possible, for the given endpoint (screening observation carried forward).

In addition, all efficacy endpoints will be presented in summary tables.

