# 5 SAMPLE SIZE DETERMINATION

The primary endpoint is the annualised rate of clinically relevant asthma exacerbations during the efficacy evaluation period (period 4). The rate of clinically relevant asthma exacerbations will be analysed using a negative binomial regression model.

From (Lanier et al. 2009) the rate of clinically relevant asthma exacerbations is expected to be approximately 1.4 exacerbations per subject per year. Over a period of 24 weeks, the number of clinically relevant asthma exacerbation in the placebo group were 0.64 per subject ( $\sim$ 0.64\*52/24 = 1.4 per subject per year).

Power calculation are both performed based on the negative binomial distribution assuming overdispersion and based on the Poisson distribution when assuming no overdispersion. Overdispersion means that some subjects will tend to have more exacerbations than others. The dispersion parameter in the negative binominal distribution is assumed to be k=0.7 (**Pavord et al.**)

Type of document Document ID	Date: Version: Status:	11-Aug-2022 4.0 Final	
INTERNAL USE	Page:	43 of 79	

**2012)**. When there is no overdispersion  $(k \rightarrow 0)$  the negative binominal distribution will become a Poisson distribution.

**Table 5** displays the sample size calculations for different values of the treatment effect expressed as the reduction in exacerbation rates for active treatment compared to placebo (100%\*(PLB-ACT/PLB)). The power is set to 90% and sample size calculations are performed using a close formula for the negative binomial regression model (Keene et al. 2007):

$$N = \left\{ \frac{z_{1-\beta} + z_{1-\alpha/2}}{\log(\mu_1/\mu_2)} \right\}^2 \times \left\{ \frac{\mu_1 + \mu_2}{\mu_1\mu_2} + 2k \right\}$$

where N is the number of subjects per treatment arm,  $\mu_1$  is the rate per subject in the given time interval for the placebo group,  $\mu_2$  is the rate per subject in the given time interval for the active group,  $1 - \beta$  is the power, alpha is the level of significance and k is the dispersion parameter.

Power	Alpha	Time for efficacy assessment (weeks)	Rate PLB	Reduction (%) 100%*(PLB- ACT)/PLB)	μ 1	μ2	k	N per arm (NB*)	N per arm (POIS)
	0.05	34			0.91	0.63		334	219
	0.05	52		30%	1.39	0.97		259	143
	0.05	86			2.29	1.61		202	87
	0.05	34			0.91	0.68		501	324
0.9	0.05	52	1.4	25%	1.39	1.04	0.7	389	212
	0.05	86			2.29	1.72		306	128
	0.05	34			0.91	0.73		814	519
	0.05	52		20%	1.39	1.11		635	339
	0.05	86			2.29	1.83		500	205

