Table 5Power calculation

PLB: placebo, ACT: active, NB: negative binominal, POIS: Poisson distribution.

If assuming a drop-out rate of 30%, a power of at least 90% and an efficacy assessment period of 20 months (86 weeks), a sample size of approximately 300 ( $\sim$ 205/0.7=293) subjects per arm should be sufficient to detect a difference in exacerbation rates of 20% when no overdispersion is present as shown in **Table 5**. In case of overdispersion defined by a dispersion parameter of k=0.7, a sample size of 300 (>202/0.7=288) subjects per arm would be sufficient to detect a difference in the exacerbation rates of 30%.

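### The confirmatory exacerbation model leaves out cohort, which largely fixes each subject's exposure to Covid-19; adding it would be a free but small gain in precision

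*SAP*

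**What the plan says.** SAP 4.2.3 models the count of exacerbations with treatment group, age group and "region as fixed effects, and the logarithm of the time in period 4 (in years) as an offset value". The SAS code in SAP 7.2.5 has the same three factors and no cohort or calendar term.

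Period 4 runs on fixed calendar dates by cohort. Protocol 3.1 has the rate "evaluated from 1 September 2018 to 30 April 2020 (cohort 1), 1 September 2019 to 30 April 2021" (cohort 2), with cohort 3 a year later again. Cohort is set by the date of screening. SAP 3 puts the boundary between the periods before and during Covid-19 at 20 March 2020.

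On the pandemic, SAP 3.2 states: "Covid-19 has impacted the trial in terms of both recruitment opportunities and impact on the primary endpoint". Protocol 15.2.2 gives the expected direction, fewer exacerbations, but no size. SAP Table 1, 4.2.6 and 4.8 repeat the analyses of the primary and secondary estimands with a two-level Covid-19 effect. The test in the hierarchy of SAP 2.1 is that of the primary estimand, for which 4.2.3 gives the model without that effect.

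**The concern.** SAP 4.1.1 adjusts for region because it expects the exacerbation rate to vary geographically. The same reasoning applies to cohort: it is known before randomisation, takes one value per subject, and separates subjects whose period 4 was almost wholly before the pandemic from those whose period 4 was wholly within it. If rates differ between cohorts and the model has no term for it, the difference is counted as between-subject overdispersion and the standard error of the treatment effect grows.

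Precision is what this trial lacks. The first sample size reassessment asked for 900 subjects and put power there at 81% (SAP 5.1), but 533 were randomised (SAP 1.2). What is at stake is the width of the interval, not the validity of the test.

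**Working it through.** **1. The plan's own figure.** Inputs from SAP 5: "The power is set to 90% and sample size calculations are performed using a close formula for the negative binomial regression model"; "the rate of clinically relevant asthma exacerbations is expected to be approximately 1.4 exacerbations per subject per year" (0.64 per 24 weeks, i.e. 1.387 per year); "The dispersion parameter in the negative binominal distribution is assumed to be k=0.7"; two-sided 5% (SAP 4.1, "all the statistical tests described in this section use a significance level of 5% and all tests and confidence intervals are 2-sided"). The target is "subjects per arm would be sufficient to detect a difference in the exacerbation rates of 30" per cent. Over 86 weeks μ1 = 0.64 × 86/24 = 2.293 and μ2 = 0.7 × 2.293 = 1.605.

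N = {(1.282 + 1.960)/ln(1/0.7)}² × {(μ1 + μ2)/(μ1μ2) + 2k} = 82.59 × 2.459 = 203.1 per arm, against 202 in the table; 202/0.7 = 288.6, given as 288. The figure is reproduced.

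**2. Share of planned period 4 after 20 March 2020.** Cohort 1: 41/608 = 6.7%. Cohort 2: 406/608 = 66.8%. Cohort 3: 607/607 = 100%.

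**3. Effect of omitting cohort.** Cohort sizes are 76, 249 and 199 randomised (Protocol Table 14, site 613 excluded), total 524. Let d be the rate reduction after 20 March 2020 (an assumption). The relative rate in cohort c is f = 1 − d × share. Take RR 0.70, 1:1 allocation and full follow-up of 608/365 = 1.666 years.

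- With cohort: variance = 1/Σ[(n/2)/(1/m1 + 1/m2 + 2k)], where m1 = rate × 1.666 × f and m2 = 0.7 m1.
- Without cohort: the apparent dispersion becomes k* = k + (1 + k)CV², where CV is the coefficient of variation of f over subjects. Variance = (1/M1 + 1/M2 + 2k*)/262, where M1 and M2 use the mean of f.

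Worked case, d = 50%, rate 1.387, k = 0.7:

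- f = 0.966, 0.666 and 0.500; mean 0.647; CV² = 0.055; k* = 0.7 + 1.7 × 0.055 = 0.79.
- Without cohort: M1 = 1.494, M2 = 1.046; variance (0.670 + 0.956 + 1.588)/262 = 0.01227; SE 0.1108.
- With cohort: information 15.3 + 41.8 + 28.4 = 85.5; variance 0.01170; SE 0.1082.
- Saving: 1 − 0.01170/0.01227 = 4.7% of variance, or about 24 of 524 subjects.

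**4. Event rates consistent with the first reassessment.** The formula in Protocol 15.2.1 can be solved for the rate that gives 81% power at 450 per arm. Drop-out before period 4 is about 3% (9 of 325 in Table 14). Mean follow-up of 1.3 to 1.67 years and k of 0.7 to 1.5 are assumed. The bracket must equal 0.97 × 450 × {ln(1/0.7)}²/(0.878 + 1.960)² = 0.97 × 7.108 = 6.895.

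- k = 0.7: expected events over follow-up = (1.7²/1.4)/(6.895 − 1.4) = 0.376; over 1.67 years, about 0.23 per year.
- k = 1.5: 2.064/(6.895 − 3) = 0.530; over 1.3 years, about 0.41 per year.

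**5. Results for assumed reductions.**

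| Reduction d | Rate 1.387, k 0.7: SE with / without cohort | Power with / without | Variance saved | Rate 0.23, k 0.7: saved | Rate 0.41, k 1.5: saved |
|---|---|---|---|---|---|
| 20% | 0.1001 / 0.1004 | 94.5 / 94.4% | 0.5% | 0.1% | 0.2% |
| 30% | 0.1023 / 0.1030 | 93.6 / 93.4% | 1.3% | 0.3% | 0.6% |
| 50% | 0.1082 / 0.1108 | 91.0 / 89.6% | 4.7% | 1.1% | 2.0% |
| 70% | 0.1176 / 0.1249 | 85.9 / 81.5% | 11.4% | 2.6% | 4.9% |

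**6. Simulation check** (rate 1.387, k 0.7, 500 runs per scenario, a quarter of subjects with shortened follow-up). Omitting cohort raised the median SE by 1.4% at d = 50% (fitted k 0.76 against 0.68) and by 4% at d = 70% (0.92 against 0.67), so somewhat less than the formula. The mean log rate ratio was practically the same with and without cohort. Under the null at d = 50%, rejection was 5.4% without and 5.8% with cohort.

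**7. In terms of power.** Scaling 81% at 900 subjects to 524 gives 2.838 × √(524/900) − 1.960 = 0.206, or about 58%. Removing 2% of the variance raises this to about 59%, and removing 5% to about 60%.

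**The case against.** The strongest reply is that the SAP already deals with Covid-19. The before/during effect addresses the pandemic directly, whereas cohort is a proxy: a third of cohort 2's period 4 (202 of 608 days) precedes the boundary. The protocol's covariates were treatment, age group and a geographic factor, and keeping them while adding labelled Covid-19 analyses late in a trial is defensible. Cohort was not a stratification factor, so nothing obliges the model to include it.

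Most of this stands, and it rules out the reading that the SAP leaves the pandemic unaddressed. It does not remove the point. The Covid-19 analyses are not the confirmatory test. SAP 4.2.6 also does not say how the effect enters the model, or how two periods from one subject would be handled. Cohort fits the existing one-record-per-subject structure without further assumptions.

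The reply is also right about size. A reader might infer that cohort is a demonstrated source of rate variation, or that adding it would recover a large part of the missing sample. The documents report no rates by cohort or by period, the direction is only expected, and region may absorb part of any difference. Larger savings need a high event rate and a severe Covid-19 effect together, and the high rate does not fit 81% power at 900 subjects: a rate of 0.6 per year or more with k up to 1.5 would give at least 88% there. The SAP calls the reassessment's rate uncertain, but it is the only trial-based evidence in the documents.

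**Conclusion.** The point holds as a minor efficiency improvement. At event rates consistent with the first reassessment (about 0.23 to 0.41 per year), adding cohort saves about 0 to 2% of the variance for Covid-19 reductions up to 50%, at most about 10 of 524 subjects, and about 3 to 5% at 70%. At the planning rate with k = 0.7, a 50% reduction gives about 4 to 5% by formula and about 3% in simulation (1.014² = 1.028). Only a reduction near 70% at that rate gives about 11% by formula.

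These figures assume an effect the documents do not quantify, the same rate ratio in both periods, and planned rather than actual exposure; discontinuation of treatment shortens period 4 and changes the shares. A reader might infer that the primary result is biased, or that an uncorrected chance imbalance of cohorts between arms invalidates it. Neither follows: the check shows no sign of bias or of a type I error problem, and chance imbalance in an unadjusted covariate is already part of the sampling error that the test allows for.

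**What to change.** Before unblinding, add cohort (three levels) as a fixed effect to the negative binomial model in SAP 4.2.3 and to the class and model statements in 7.2.5, and list the change in 4.8. Keep the before/during Covid-19 analyses as additional, and state in 4.2.6 how the effect enters the model and how two periods from the same subject are treated. If the confirmatory covariates are to stay as they are, the fallback is to pre-specify the model with cohort as a sensitivity analysis. The cost is 2 degrees of freedom and a few lines of text and code; cohort follows from the screening date, so no new data are needed.
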